#### Schedule of assessment (if applicable)

---

[Schedule of assessments v.3.docx](#)

\*required

**What is the anticipated completion date for the study?**

---

12-31-2023

\*required

## Study Procedures

---

*Check all that apply*

- Survey/Questionnaires

Attach survey(s)/questionnaire(s)

---

[Participants personal information.docx](#)

[Study questionnaires LKM.V4.docx](#)

How will these be administered?

---

- Online

- Hard copy

Telephone

Other

- Interviews

\*required

Attach script

---

[Guide for Quantitative data collection v2.docx](#)

[Orientation Guide.docx](#)

[LKM Mindfulness Orientation Video](#)

[LKM Intervention Video](#)

- Audio Recording

\*required

Provide details of activities to be recorded and who will be recorded.

---

Whole focus group interview will be audio recorded, given all the participants unanimously agree to it. Focus group guide is attached below. We will ask the following before hitting the record button: "May I tape the discussion to facilitate its recollection? (if yes, switch on the

recorder, everyone should be comfortable being recorded, and we will not collect identifying information during the focus group and deter participants from using their names) (if no, we will write the notes to the best of our ability and ask questions as needed)."

#### Video Recording

- ✓ Diaries or Journals

\*required

**Provide details of diary or journal entry requirements.**

---

Each participant in the intervention group is asked to write about their experience right after their daily meditative practice. We encourage them to answer all questions but answering any question is voluntary. These questions will guide the daily entry: How was your experience during the meditation? How long did you meditate today? Explain how you felt following the guided recording? What is your general emotion after the practice? What do you feel was the most challenging during the meditation practice or to continue the practice? Weekly Entry: Along with the daily entry, there would be extra questions for weekly entry: How is your behavior impacted by meditation? Do you have better controlled over your emotions? How do you feel for yourself and others now? Have you made any lifestyle modifications, such as better eating and drinking habits? Please explain. Has your sleep improved?

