The orientation is about 10-20 minutes (with both in person and recording) and recorded LKM training is about 30-35 minutes (video links provided under interview section as attachments). We will also have a Questions and Answers session, which could take up 10-20 minutes. Participants will be then given the link to fill out the post intervention questionnaires on their own and if they request paper and pen version, those would be available as well.

After 3 weeks of intervention, we will call to set up an appointment to meet both intervention and control group to collect data for 4 week data collection. At this data collection session, we will also collect 30-day journal folders. At this time, we will also ask for **8-10** volunteers for focus group study (we will have two group of 4-5 participants) and once we have their permission, we will set up another appointment for focus group interview, which may take up to 90 minutes at either OLLI campus or apartment's media room. We will also set up an appointment for control group for their LKM training after collecting time 2 data from them. We will do a month follow-up again at 8 week for intervention group and 4week post-intervention data collection for control group.

There are three areas of outcome measures we are aiming to determine: feasibility, acceptability, and initial efficacy:

(1) feasibility of collecting measures of self-compassion, loneliness, depressive symptoms, anxiety, and cognitive function; (2) acceptability of the intervention (i.e., satisfaction, adherence, recruitment, and retention rates); and (3) initial efficacy (i.e., changes in loneliness along with self-compassion, depressive symptoms, anxiety and cognitive function at immediately post-intervention, at 30 and 60 day follow-up). We will evaluate feasibility through participants' satisfaction, their continued use of intervention after the study completion, how appropriate the intervention was for them, their positive or negative effects associated with the intervention. We will also assess their active and continual participation, retention rates, participation rate, and missing data on collected measures. We will also conduct two focus group with **4-5 participants in each group** at the end of the study to determine the feasibility of the study and how we can further improve the intervention for future research. PI will transcribe the qualitative interviews.

\*required

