**What procedure(s) will be utilized to prevent/minimize any potential risks?**

---

Given the potential risk information we have, we will make sure to teach our participants about potential risks and how to handle them should they arise. We will ask the participants to write down these experiences in their daily diaries, and if it starts to bother their daily activities, we will ask them to stop the practice.

Participants may feel uncomfortable during their meditation practices as they become more aware of their thoughts and emotions as they become more mindful of their surroundings and body responses. During the orientation session, participants will be instructed on how to deal with these thoughts safely. Participants will be encouraged to keep their eyes open if closing them feels uncomfortable. They will also be told that thoughts are normal, but guided meditation will help them focus back on the meditation. If they cannot focus back on the meditation, then that is normal as well. We will let them know that their comfort is important and should they feel any discomfort, they can stop the meditative practice and come back at a later time. They also have the option to stop the intervention at anytime and withdraw from the study.

Should they have any discomfort with answering the questions, they can skip the questions. They also have the option to stop the study at anytime.

They will be encouraged to approach the PI to discuss any concerns. The PI's mobile telephone number and email will be provided to the participants during the orientation to contact the PI.

\*required

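### Three of the five weekly diary items are worded towards improvement and none asks about worsening, so the diary's evidence on positive and negative effects leans to benefit

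*Combined protocol and SAP*

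**What the plan says.** The section *Provide details of diary or journal entry requirements* lists five daily questions and then adds weekly ones: "Along with the daily entry, there would be extra questions for weekly entry". The five weekly items are:

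1. and 2. "How is your behavior impacted by meditation? Do you have better controlled over your emotions"
3. "How do you feel for yourself and others now"
4. "Have you made any lifestyle modifications, such as better eating and drinking habits", followed by a request to explain
5. "Has your sleep improved"

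The daily list includes open questions on the meditation experience and on feelings afterwards, and one on difficulty: "What do you feel was the most challenging during the meditation practice or to continue the practice". Answering any question is voluntary.

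Two other places bear on what the diary is for. Under *How will you conduct this study?*, the feasibility evaluation includes "their positive or negative effects associated with the intervention", with no instrument named for it. Under *What procedure(s) will be utilized to prevent/minimize any potential risks?*, the protocol says of difficulties arising from practice: "We will ask the participants to write down these experiences in their daily diaries".

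**The concern.** An outcome described as positive or negative needs questions that can return either answer on equal terms. Most of the weekly items name only the favourable direction, and one takes an effect of meditation for granted. A participant whose sleep or emotional control got worse is not asked to say so, and the short answer 'no' looks the same as no change. If the diary is summarised as evidence on effects, its weekly part can show how many people reported benefit but not how many reported deterioration. A pilot is meant to inform refinement of the intervention, so unwanted effects are as useful to it as benefits.

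A secondary worry concerns the efficacy scales. Only trained participants keep the diary before the week-4 assessment, so only they are repeatedly prompted to look for improvement before completing self-report scales on related topics.

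**Working it through.** The plan gives no figure on this point, so the check is a classification of the items, a statement of what the answers can identify, and an ordering of events by arm.

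**Step 1: direction of each weekly item** (diary requirements section)

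- Behaviour: presupposes an effect and attributes it to meditation, but leaves the direction open.
- Control over emotions: names improvement only.
- Feelings for self and others: neutral.
- Lifestyle: leans to improvement through its example; an explanation is invited.
- Sleep: names improvement only.

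Count: 3 of 5 towards benefit, 1 of 5 presupposing but undirected, 1 of 5 neutral (3 + 1 + 1 = 5). Items asking about worsening: 0 of 5.

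**Step 2: what a short answer identifies.** Suppose n participants answer the sleep item and Y say yes. The n − Y who say no are the unchanged plus the worse, so the number worse lies anywhere from 0 to n − Y. With the planned 50 in the intervention arm all answering, that range is 0 to 50 − Y. Free text can narrow it, but only for those who choose to elaborate.

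**Step 3: what the daily items add.** Of the five daily items, one asks how long the person meditated. Three are open (the experience, how the person felt following the recording, general emotion afterwards). One asks about challenges in doing or continuing the practice. Distress around a session can therefore be written down on any day. None of the five asks about sleep, eating and drinking, or control over emotions during the week, which are the subjects of the benefit-worded weekly items.

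**Step 4: timing by arm** (*How will you conduct this study?*). The diary is handed out after training and collected at the week-4 data session. Controls are trained only after their own week-4 data are taken. A 30-day diary holds about 30/7 ≈ 4 weekly entries, so before or at the week-4 self-reports exposure is at most about 4 entries in the intervention arm and 0 in the control arm.

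**Step 5: illustration of priming.** The documents give no size for a reporting shift, so values are assumed. For a simple week-4 comparison at 50 per arm with no attrition, a pure reporting shift of δ SD moves the test statistic by δ/√(2/50) = δ/0.2. The two-sided 5% error becomes P(Z > 1.96 − δ/0.2) + P(Z < −1.96 − δ/0.2):

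- δ = 0.1: shift 0.5, error 0.079
- δ = 0.2: shift 1.0, error 0.170
- δ = 0.3: shift 1.5, error 0.323

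This shows only what such a shift would do if present. Nothing in the documents indicates which value applies, or that it differs from zero.

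**The case against.** Four stronger readings are tempting, and the documents do not support them.

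- *The weekly diary asks only whether things improved.* It does not. One item is neutral and another leaves direction open.
- *The diary cannot record harm.* It can. The daily entry has open questions, the challenge item invites negative content, and the risk section asks participants to write down difficult experiences. The questions guide written entries and are not tick-boxes, so anyone may write that sleep got worse.
- *The feasibility account as a whole is biased upward.* This is not established. The diary is not named as the source, let alone the only source, for positive or negative effects. Intervention evaluation questions at the end of the intervention, week 4 and week 8, reasons for dropping out, and the focus groups may all capture them. The questionnaires and guides are attachments that are not available here.
- *The week-4 efficacy results are biased by the prompts.* This cannot be shown. Diary writing is taught as part of the intervention, alongside instruction on its importance and weekly reminder calls. Unequal expectation between arms is largely inherent in an unblinded waitlist design. Balanced prompts would still be answered by one arm only, so rewording would not remove the asymmetry. The count of about four exposures is also an upper estimate, because answering is voluntary.

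All of this narrows the point. What it leaves standing is the difference between allowing harm to be volunteered and asking about it. The weekly prompts ask about benefit and leave worsening to the participant's initiative, in a document that the protocol itself uses to record unpleasant experiences.

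**Conclusion.** The point holds as a measurement problem confined to the weekly diary items. Three of five lean to improvement, one presupposes an impact, and none asks about worsening, so a bare 'no' merges unchanged with worse. This tilts the diary's contribution to the positive-or-negative-effects part of feasibility towards benefit. How far it tilts that outcome overall is unknown, because the other instruments' content is not shown and no source is specified. Priming of the week-4 self-reports is possible, of unknown size, and only a supporting reason.

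The conclusion rests on the item wording as printed in the diary requirements section and assumes that diary responses will be used in describing effects, which the protocol implies but does not state. The change is worth making because it is specific and nearly free.

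**What to change.** Reword the weekly items in both directions against a fixed reference point:

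- 'Compared with before you began the practice, is your sleep better, the same or worse?'
- The same three options and reference point for control over emotions and for eating and drinking.
- 'Have you noticed any change, good or bad, in your behaviour? If none, write none.'

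The neutral item can stay. The reference point matters: against the previous week, someone whose sleep worsened in week 1 and stayed poor would answer 'the same' in weeks 2 to 4, which would hide a sustained worsening.

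State which instruments supply the positive-or-negative-effects outcome. Report the better, same and worse responses descriptively alongside the evaluation questions and focus groups, without treating the diary as an efficacy scale.

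Cost: one reprinted diary page, with no added visits. The protocol form requires changes to approved assessments to go through a modification submission, and one is already being filed for the sample size. Diaries completed under the old wording must be reported separately.

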#### Still Photography

- ✓ Focus Group

\*required

**Attach focus group script or guide.**

---

[Focus Group Interview Guide.docx](#)

\*required

**How many participants will be in each focus group?**

---

5

\*required

**Provide the number of times each participant will take part in a focus group.**

---

1

#### Observation

#### Secondary Analysis

#### Other

\*required

**Project Site(s):**

---

*Where will you conduct this study?*

*NOTE: If the project site is other than UNLV or online, a Facility Authorization Letter must be submitted for each site. You can find a template letter [here](#).*

---

UNLV campus

\*required

**Specify which campus:**

---

Maryland Campus

Shadow Lane/Medical Campus

Other

\*required

**Please specify**

---

Osher Lifelong Institute

External Collaborating Site(s) (e.g. collaborating site where study procedures are being conducted)

External Public Site(s) (e.g. coffee shop, library, etc.)

CCSD School(s)

International Site(s)

Online

Other (e.g., Non-CCSD schools)

Provide a signed Letter of Authorization.

---

[UNLV Letter of Support HHOVV.pdf](#)

[OLLI letter of support.pdf](#)

[Facility authorization letter McKnight apartment.pdf](#)

\*required

### Is this study a clinical trial?

---

*NIH defines a clinical trial as a research study in which one or more human subjects are prospectively assigned to one or more interventions (which may include placebo or other control) to evaluate the effects of those interventions on health-related biomedical or behavioral outcomes.*

Yes

\*required

Provide the CT.gov number (NCTID).

---

NCT05350449

Attach a study protocol.

---

No

\*required

### Describe the consent process.

---

Include:

- Who is obtaining consent?
- When and where will consent be obtained?
- How will the consent form be distributed to the participant?
- If obtaining signed consent, how will you collect the signed consent form?
- Who will be providing consent? (e.g., the subject, the parent, etc.)
- If minors are subjects, include how parent permission and assent will be obtained.

*NOTE: If identifiable information will be published, shared or disseminated, the consent form must describe this for the subject.*

- Who is obtaining consent?: PI or trained research assistant with CITI training. The research assistants will be hired after funding support.
- When and where will consent be obtained?: Participants' home or mutually agreed upon venue. We will make sure that the venue is a private and secure area.
- How will the consent form be distributed to the participant?: A copy of the consent form will be provided to the participants. We will explain the information of the consent form to the participants, give them time to read and ask any questions. Once we are sure that participants understood the study and procedures involved, we will ask them to sign the informed consent. a copy of which will be provided to them.
- If obtaining signed consent, how will you collect the signed consent form?: It will be collected face to face.
- Who will be providing consent? (e.g., the subject, the parent, etc.): The subject will be providing the consent.

\*required

### Select all that apply for your consent process

---

Informed consent (with signature)

✓ Note: Signed consent may be a physical signature on a hard copy consent form, an electronic signature, or a typed name (for non-FDA regulated research).

Check all that apply

---

Parent Permission Form(s)

A assent Form(s)

Informed Consent Form(s)

Informed Consent Form(s) with HIPAA authorization.

*Attach informed consent forms here.*

---

[Research-InformedConsentForm.v6.docx](#)

Waiver of Documentation of informed consent (i.e. waiving the requirement to obtain signed consent)

*Note: A Waiver of Documentation of Informed Consent is when you are still conducting a consent process, but you are not obtaining signed consent.*

*Examples: verbal consent, clicking a radio button to indicate consent, providing an information sheet, etc.*

Waiver of informed consent

*Note: A Waiver of Informed Consent is when you are not conducting a consent process at all.*

Alteration of informed consent (use for deception/incomplete disclosure of purpose).

\*required

### **Compensation**

---

Will subjects be paid or otherwise compensated for research participation?

---

*NOTE: UNLV has implemented the Forte Research Payments System as the central system to electronically manage incentives for UNLV research participants. The system will pay research participants via VISA credit card, check, or direct account deposit.*

*Please contact [contact] if you have questions about the use of Forte, to begin the process, or want to receive a waiver in order to use an alternative payment method.*

Yes

Describe the amount and nature of any compensation to subjects. Include gifts, research credit, gift cards, etc.

---

Participant Incentives (amount listed is per participants): Intervention Group: \$25 per participants for baseline data collection; mp3 device with micro sd card (total of \$35 value for guided meditation, and they will keep the mp3 device and return it is not expected) after orientation and first intervention training; \$ 10 per participants after LKM intervention training; Post intervention data collection and 30 day diary entries will be compensated with \$30. At one month follow-up data collection, participants time will be compensated at \$20 per participants. Control Group: \$25 per participants for baseline data collection; \$20 per participants after time 2 data collection before intervention. During intervention, mp3 device with micro sd card will be provided. \$10 per participants after LKM intervention training; Post intervention data collection and 30 day diary entries will be compensated with \$30. At one month follow-up data collection, participants time will be compensated at \$20 per participants. Focus Group: \$25 per participants for 90 minutes interview.

No

\*required

Indicate the method of payment.

---

Forte System Gift Card

*The Forte Research Payment System asks for participant identifiers (name, gender, email, mailing address, and date of birth). In the consent form, please include that participants may be asked to provide their name, gender, email, mailing address, and date of birth for compensation purposes. Specify if these identifiers will or will not be linked to their study data.*

---

Research Credit

Other

\*required

When and how is the compensation provided to the subject?

---

*Most studies require partial compensation be given for partial participation. Please address this in your answer.*

The description how much compensation is provided above. We will provide them with described amount at each face to face meeting by adding designated amount in their Forte prepaid card. For partial participation, partial compensation will be provided. For example, they will receive \$ 25 for baseline data collection and will not receive further compensation if they did not participate after the baseline data collection. If they took the training on intervention but chose to decline at time 2 data

collection, they will be allowed to keep mp3 player and sd card but will not receive \$10 as no data will be collected. If participants did not complete the journal at all but provided data for time 3 data collection, they will receive \$20 for data collection but not whole \$30.

\*required

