Except for demographic information, other data and some intervention evaluation questions will also be collected at the end of the intervention, at 4 week and 8 week. There will be one extra data collection for control group before they get their intervention at 4 week. If for any reason participants refuse to participate during any part of the study, we will collect the reasons for their premature dropping out of the study. Some of the questions that will be asked to those who drop out of the study prematurely are in "Guide for Quantitative Data Collection" attachment.

The intervention primarily involves orientation and mindfulness practices such as proper posture, breathing techniques. We will also teach them the importance of the intervention and daily

practices, how to deal with thoughts that may arise during the meditation practice, and encourage them to write about their daily meditation experiences in the diary provided to them. We will also teach them loving-kindness meditation and provide them with guided meditation on an MP3 device, which they do not have return upon completion of the study. The orientation and intervention will happen in the lobby area, common space, or OLLI classroom in a group setting. The LKM recording will consist of mindfulness practice where they are guided to focus on compassion and kindness for themselves and others. Recording for both brief orientation and LKM are attached. After intervention session is over, participants are encouraged to practice guided meditation daily using the mp3 device for 20-25 minutes on their own at time appropriate for them. They will be encouraged to write their experience in the diary after the practice, which can take from 5 to 10 minutes daily. The diary will be a small folder with some questions to guide their entries daily. Please see dairy or journal requirement attachment for more information. The diary will be given to the participants after the intervention training. There will be weekly reminders via phone call to practice meditation daily and write their experiences in the diary. Weekly call will be around 5-10 minutes weekly for four weeks.

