### **Where will *identifiable* and *de-identified* data be stored?**

---

*For review/audit purposes, a copy of all records must be kept in a location accessible to the PI on UNLV property.*

*A USB Drive cannot be used for storage of the data. A HIPAA compliant storage solution must be utilized, accessible to both the student and PI. No PHI should be stored on a USB drive.*

Indefinable paper records will be kept at secure storage location at UNLV school of nursing research office file cabinet. De-identified data are collected in online Qualtrics software. We will collect identifying information in paper separately, so it will be linked to Qualtrics data by subject code number. This code number is used to combine different time points data. When this data is downloaded in SPSS software, it will be stored in UNLV PI computer which is password protected. This will be accessible only to the PI and

UNLV research data sharing policy will be followed when sharing the de-identified data to a statistician, mainly for analysis purposes.

\*required

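### Visit labels and clocks conflict between arms, and the stated two-group by four-time model fits controls only on a clock that leaves out their untreated week-4 score

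*Combined protocol and SAP*

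**What the plan says.** **Meaning of *time 2*.** Under Compensation, the partial-payment rule takes a participant who has already been trained: "If they took the training on intervention but chose to decline at time 2 data" and then "collection, they will be allowed to keep mp3 player and sd card but will not receive \$10 as no data will be collected". In the same section's payment lists, $10 is what is paid after the meditation (LKM) training. The rule then uses *time 3* for the visit at which the journal is due. The control payment list in the same section pays $20 "per participants after time 2 data collection before intervention". The procedures (How will you conduct this study?) agree with that list: "We will also set up an appointment for control group for their LKM training after collecting time 2 data from them". The time-commitment list names a *Time 2* visit for the control group only, without a week and without saying whether it precedes training.

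**The controls' last visit.** The procedures say: "We will do a month follow-up again at 8 week for intervention group and 4week post-intervention data collection for control group". No later control visit is scheduled there. Compensation pays controls $30 for the post-intervention visit with the 30-day diary, and then $20 for a one-month follow-up. Earlier in the procedures, all participants are measured at the end of the intervention, at 4 weeks and at 8 weeks, and "There will be one extra data collection for control group before they get their intervention at 4 week". The starting point of those weeks is not stated.

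**Model and linkage.** The sample-size text plans a between-within repeated measures ANOVA with two groups and four occasions: baseline, straight after the intervention, one month and two months. On data handling, the storage section says of the participant code: "This code number is used to combine different time points data".

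**The concern.** A two-group repeated measures model needs one time index shared by both arms. In a waitlist trial, study week and weeks since own training differ for controls, and the plan moves between the two without saying which applies. The same label can then name a visit after training in one arm and before training in the other.

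At stake is the contrast behind Objectives 2 and 3, whose hypotheses are set at 30 days. Controls are untreated at only one post-baseline visit, at study week 4. If the analysis index does not line that visit up with the intervention arm's week-4 visit, the randomised comparison of meditation with no meditation is lost. Separately, the text does not settle whether up to 50 controls have a further follow-up that Compensation pays for.

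**Working it through.** **1. The plan's own figure.** Inputs from the sample-size text: f = 0.2, alpha 0.05, power 90%, 2 groups, m = 4 occasions. Assumed, because not given: correlation rho = 0.5 and sphericity (epsilon = 1). For the group-by-time effect, lambda = f² × N × m / (1 − rho), with df1 = (2 − 1)(m − 1) and df2 = (N − 2)(m − 1). At N = 46, lambda = 0.04 × 46 × 4 / 0.5 = 14.72 with df 3 and 132, and power is 0.903. At N = 44 it is 0.888. So 46 reproduces. Visit labels do not enter this calculation.

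**2. Visits by study week.** This assumes controls are trained at about week 4, directly after their untreated visit. A plus sign means straight after training.

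| Order of visit | Intervention | Control |
|---|---|---|
| 1 | 0 | 0 |
| 2 | 0+ | 4, untreated |
| 3 | 4 | 4+ |
| 4 | 8 | 8 (4 weeks after own training) |
| 5 | none | about 12, only if the paid follow-up exists |

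The partial-payment rule's *time 2* and *time 3* match intervention visits 2 and 3 (weeks 0+ and 4). The procedures' *time 2* is control visit 2 (week 4, untreated). The rule cannot describe a control, who has not been trained before *time 2*.

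**3. Payments as a cross-check on the number of visits.** Intervention: 25 + 10 + 30 + 20 = $85 over four payments. Control: 25 + 20 + 10 + 30 + 20 = $105 over five. The fifth control payment is for a one-month follow-up after the diary visit: week 4 (training) + 4 (diary visit) + 4 (follow-up) = about week 12. The procedures give controls four occasions, ending alongside the intervention arm's week 8. The sentence about one extra control visit fits four occasions if weeks run from study start, and five if they run from own training.

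**4. Filling the four-occasion model for controls.** On study time, controls have no visit at 0+, so the second occasion is empty. On own-training time, the occasions are 0, 4+, 8 and about 12; the last is filled only if the extra follow-up exists, and the untreated week-4 score has no place.

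**5. What each alignment estimates.** Let the effect be e straight after training, d at four weeks and g at eight weeks, the same in both arms, with no change in untreated controls. Expected differences in change from baseline, intervention minus control:

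- Study week: week 4 gives d − 0 = d; week 8 gives g − d.
- Own-training time: e − e = 0, d − d = 0, g − g = 0.
- Order of visit: second e − 0 = e; third d − e; fourth g − d.

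**6. Power for the week-4 contrast alone.** Keeping f = 0.2 with m = 2 (an assumption, since f was set for four occasions) and rho = 0.5, N for 90% power is 68. Power is 75.6% at 46, 86.1% at 60 and 97.7% at 100. For rho from 0.3 to 0.7, power at 100 complete cases is 91.7% to 99.9%.

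**The case against.** The strongest reply is that *time 2* may simply mean each arm's second data collection. The partial-payment rule names no arm, and the other uses are tied to the control group. That reading is coherent and should be granted. It still leaves one label for two different visits, and a payment rule that cannot apply to controls as written.

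A reader might infer that the plan joins the arms by time number and so pairs the wrong visits. The documents do not support that. The storage section describes linking one person's records by code, which is sound, and no text aligns arms by label.

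A reader might also infer that the time-commitment list ends both arms at week 8, or places the controls' *time 2* before training at week 4. It does neither; its 4-week and 8-week entries name no arm and no clock. Nor is week 12 written anywhere.

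Two further points stand. The procedures do state a common 4-week data collection for both arms, so the right visit will be collected. And the attached schedule of assessments and questionnaires were not available; they may define the labels. That could limit the harm, but it would not remove the conflict between the procedures and Compensation.

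What the reply does not answer is the model. As labelled, its occasions can be filled for controls only on own-training time, even though the needed week-4 data will exist.

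**Conclusion.** The concern holds as a conflict of labels and clocks that leaves the efficacy contrast undefined. *Time 2* has two meanings, and the procedures schedule no control visit to match the follow-up that Compensation pays for. The four-occasion model, taken as labelled, compares trained with trained.

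The size depends on the alignment chosen: the same data have an expected between-arm difference of d at study week 4 and 0 on own-training time. This assumes equal effects in both arms, no change in untreated controls, and control training at about week 4. It illustrates what is at risk; it is not an estimate of bias in a specified analysis. The N of 46 is arithmetically unaffected. The trial is a feasibility pilot, so this bears on its preliminary efficacy aim and not on feasibility or acceptability.

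**What to change.** 1. Label every visit by weeks since randomisation, identically in both arms, in the protocol and the questionnaire. Mark post-training questionnaires separately by arm, and hold weeks since own training as its own variable.
2. State that arms are compared by study week, with week 4 versus baseline (controls before training) as the efficacy contrast. Report later visits as post-crossover.
3. Replace *time 2* and *time 3* wherever they occur.
4. Reconcile the procedures, the time-commitment list, both parts of Compensation and the attached schedule on whether controls have a follow-up beyond four weeks after their training. Which it should be is for the investigator to decide.

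The cost is wording in about five places, the questionnaire labels and one IRB modification. Items 1 to 3 need no new visits or participants. Item 4 settles whether a $20 payment applies to up to 50 controls (20 × 50 = $1,000 at most).
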